## **Secondary Outcomes**

Root resorption was evaluated, as a secondary outcome, using the periapical radiographs of the canines before canine retraction and after three months. One operator, using parallax technique made all digital periapical radiographs by the same X-ray machine (RXDC eXTend, Myray, Italy), set up at 7 mA, 60 kV with an exposure time of 0.32 second. DIGORA Optime digital imaging plate system with its phosphor plate films (Soredex, Finland) was used in this study. Intraoral XCP film holders were used (Dentsply Rinn, Elgin, USA). Root resorption was measured using DIGORA for Windows 2.8 software, (Soredex, Finland). All radiographs were calibrated by 15.63 pixels per mm according to the manufacturing instruction. Root resorption in millimeter (mm) was measured by the difference between root length at baseline (R1) and after three months (R2). The reference point was the midpoint of mesial and distal cementoenamel junction (CEJ). The root length was calculated from root apex to the midpoint of cementoenamel junction (CEJ).

Periodontal index and plaque index were also evaluated clinically in both upper

canines and second premolars before canine retraction and after three months according to Löe. Both pain intensity and interference were evaluated using Visual Analog Scale (VAS) from 0 to 10 Numeric Rate Scale (0= no pain, 10= severe pain). The participants filled out a questionnaire to assess the pain intensity immediately, after 1 hour, 12 hours, day 1, day 3, day 5 and day 7 following MOP intervention. Pain interference with daily life was assessed after MOP intervention on 1, 3, 5 and 7 days in which patients were asked to provide their subjective answers of pain during eating, pain awakened them at night, the feeling of discomfort and swelling on the surgical side. Numeric Rate Scale was also used to rate the level of satisfaction (0= not satisfied, 10= very satisfied) and easiness of MOP procedure (0= very easy, 10= very complicated). Moreover, the patients were asked if they were willing to repeat the procedure and recommend to a friend using categorical data (Yes or No). There were no changes to the outcome measures after trial commencement.

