**NCT Number 02473471**

**February 21, 2017**

## **MATERIAL AND METHODS:**

### **Trial design and any changes after trial**

#### **Commencement**

This study was a split mouth randomized clinical trial with a 1:1 allocation. Methods were not changed after trial initiation.

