### **Clinical Micro-osteoperforations Procedure**

MOPs were performed when the canines were ready to be retracted. The patients were asked to rinse their mouth twice by chlorhexidine for 1 minute. Local anesthesia was then given (2% lidocaine with 1:100,000 epinephrine, Septodont, France). MOPs were also performed by one investigator as judged by the randomization process either on the right or left upper canines as the following:

- a) MOP with 1.5 mm width and 3 to 4 mm depth inside the bone was applied. MOPs were performed using miniscrews (Aarhus Mini-implant system, American Orthodontics) of 1.5 mm diameter and 6 mm length in 3 points distal to canine.
- b) The points of screws insertion were demarcated by bleeding points using the calibrated periodontal probe. One row consisting of 3 holes was made distal to the canine.
- c) For standardization of the protocol, the exact location of screw insertion was determined as the following: the first dot was located 3mm distal to canine and 6 mm from the free gingival margin. The second point was marked 5 mm from the first one. The net distances between MOP after insertion of 1.5 mm diameter miniscrews were 3 mm between each

hole and 2 mm away from the contact point and 5 mm away from the free gingival margin (Figure 1).

- d) The miniscrew length of 6 mm was used to be inserted 3 to 4 mm deep into the bone and to account for the thickness of the soft tissue of about 2 to 3 mm.

After application of MOP, the extraction space was started to be closed using NiTi close coil spring connecting from the miniscrews between upper second premolar and first molar to power arm extended from the vertical slot of the upper canine bracket (3M Unitek, 9mm, 150g) (see Figure 3). The force was measured by force gauge (Correx, Dentaurum, Germany) at the day of application to ensure the constant and equal amount of force between all subjects and also between experimental and control sides.

After the intervention, the patients were instructed to take analgesics, such acetaminophen/Tylenol, only if necessary. Anti-inflammatory NSAIDs were avoided because of their known effect on tooth movement. Maintaining good oral hygiene and using chlorhexidine 0.2%, twice a day for five days, were recommended.

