#### **Statistical analysis (primary and secondary outcomes, subgroup analyses)**

Statistical analysis was accomplished using the Statistical Package for the Social Sciences computer software (SPSS 20.0, SPSS Inc., IL, USA). Probability values equal or less than 0.05 were considered significant. Independent sample t-tests were calculated to analyze the results of the primary outcome and secondary outcomes to compare the difference between MOP and control sides. Similarly, independent sample t-test was performed to compare the amount of root resorption before and after three months in MOP and control sides separately. Chi-square was used for analysis of categorical data including the willingness to repeat the procedure and recommend it to a friend. Descriptive statistics were used to describe the satisfaction and ease of the procedure.

Reliability coefficient (Cronbach's Alpha) was used to evaluate the reliability of measurements of primary outcomes. One examiner did all measurements, and all subjects were randomly selected. Six of 3D superimposed digital models had been chosen randomly. Superimpositions on the rugae area and canine displacement were measured twice within 2-week interval. Reliability coefficient (Cronbach's Alpha) was 0.95, showing excellent superimpositions and measurement agreement.

For intraoral measurements, intra-examiner reliability was done in the lower arch after reaching 0.019x0.025 stainless steel arch wire and teeth were in a passive state; all cases were non-extraction in the lower arch. Six of subjects were selected randomly, and measurements were done twice with the 2-week interval. Measurements were done from the upper mesial wings of the lower canine bracket to the upper distal wing of the lower second premolar bracket. Reliability coefficient (Cronbach's Alpha) was 1.00, indicating excellent measurement agreement.

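### Pain falls under the MOP-versus-control t-test, but no control-side pain rating is described, so the planned comparison has no stated comparator

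*Combined protocol and SAP*

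**What the plan says.** The design is within-patient: "This study was a split mouth randomized clinical trial with a 1:1 allocation".

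**Collection (Secondary Outcomes).** Intensity and interference are both placed on a 0 to 10 scale. For intensity: "The participants filled out a questionnaire to assess the pain intensity immediately", then at six later times up to day 7, all timed from MOP. For interference: "Pain interference with daily life was assessed after MOP intervention on 1, 3, 5 and 7 days", covering pain on eating and then "pain awakened them at night, the feeling of discomfort and swelling on the surgical side". The section mentions no rating of the control side.

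**Analysis (Statistical analysis).** Independent-samples t-tests are used "to analyze the results of the primary outcome and secondary outcomes to compare the difference between MOP and control sides". Two groups of items are handled differently. The yes/no acceptability questions go to chi-square, and for two ratings of the procedure "Descriptive statistics were used to describe the satisfaction and ease of the procedure". Pain is in neither group.

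**Force (Clinical Micro-osteoperforations Procedure).** Coil-spring space closure follows MOP, and the force is checked to give an "equal amount of force between all subjects and also between experimental and control sides".

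**The concern.** A test between two sides needs a value from each side. The collection text gives a pain value whose side is either unstated or surgical, while the analysis text calls for a control value as well. Someone following both sections would either have no second sample or would have to build one in a way the plan does not define.

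What is at stake is any statement about the pain that MOP adds. The control side in a split-mouth trial receives the same retraction without MOP, so the side difference is the only contrast here that isolates MOP. Without it, a low score could be read as showing that MOP adds no pain, and a high score as showing that MOP hurts. Neither reading would be supported, because orthodontic force itself may cause pain in the same week.

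There is a second problem if both sides were rated. An independent-samples test treats two ratings from one patient as if they came from two people.

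**Working it through.** The plan gives no figure for pain, so there is none to reproduce. The check is mainly a reading of sections side by side.

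**1. Does the side comparison cover pain?** Pain sits under Secondary Outcomes and is numeric. The analysis sentence names the secondary outcomes without exception. Only the categorical items and the satisfaction and ease ratings are treated otherwise. So yes.

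**2. Is a control-side value described?** The closing phrase of the interference list can be read in two ways.

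| Reading of the surgical-side phrase | Pain intensity | Eating, night waking, discomfort | Swelling | Control value described? |
|---|---|---|---|---|
| Qualifies only the last item(s) | side not stated | side not stated for some or all | surgical side | no |
| Qualifies the whole list | side not stated | surgical side | surgical side | no |

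Both readings give the same answer.

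**3. Is the silence just the document's style?** Not throughout. Under Primary Outcomes, the caliper distance is said to be taken on the right and the left. In the analysis section, root resorption is described for each of the two sides. The pain items carry no such statement.

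**4. What can each kind of rating show?** Let *r* be the mean pain from retraction on a side and *m* the mean extra pain from MOP. Assume the two add, and that *r* is equal on both sides because the force is equal.

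- Surgical-side rating: expectation *r* + *m*. This is one equation in two unknowns, so *m* is not identified.
- One whole-mouth rating: some mixture of *r* + *m* and *r*, with weights chosen by the patient. Again *m* is not identified.
- Separate ratings: (*r* + *m*) − *r* = *m*. The side difference identifies it.

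The document does not say whether the first, immediate rating came before or after the coil was attached. If before, it might be free of coil force, but it would still have no control value for the stated test.

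**5. If both sides were rated, does the choice of test matter?** Let each side have standard deviation σ, with within-patient correlation ρ and *n* patients. The independent test uses a standard error of σ√(2/*n*). The standard error of the paired difference is σ√(2(1 − ρ)/*n*). Their ratio is √(1 − ρ). The plan gives no ρ, so these values are assumptions:

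| ρ | √(1 − ρ) |
|---|---|
| 0 | 1.00 |
| 0.3 | √0.7 = 0.84 |
| 0.5 | √0.5 = 0.71 |
| 0.7 | √0.3 = 0.55 |

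With positive correlation, the independent test overstates the standard error and can miss a real side difference in pain.

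**The case against.** The strongest reply is that this is an inference from silence. The questionnaire is not reproduced, and a single form could have had right and left columns. The stated MOP-versus-control comparison is itself some evidence that ratings by side were intended. That stands. A reader might infer that no control-side rating was ever taken, or that every patient gave exactly one rating; the documents show neither. They show only that none is described.

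A reader might also infer that pain on eating and night waking cannot belong to a side. The documents do not support that. A patient can plausibly say which side hurts when chewing, and on one reading of the list the plan itself ties all the items to the surgical side. Night waking is harder to assign, but that is a matter of judgement.

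Nor can the number of affected tests be counted. The plan does not say whether pain is tested at each time and for each item, or summarised first.

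It can further be said that pain sits beside satisfaction and ease, which describe acceptability of the procedure and need no control. That would be a sound reason to report pain descriptively. But the plan reserves descriptive treatment for satisfaction and ease and leaves pain in the side comparison.

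Finally, simultaneous retraction on both sides is implied by the equal-force statement and the bilateral measurements, and is not stated outright.

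**Conclusion.** The concern holds in this form: the collection and analysis sections do not match for pain. As written, the MOP-versus-control pain comparison has no described comparator, and neither a single rating nor a surgical-side rating can separate MOP pain from retraction pain.

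It reaches every pain intensity and interference item, whatever the number of tests. It does not touch the primary outcome or the other secondary outcomes. It should be corrected, because a named secondary outcome cannot be analysed as specified from the data described.

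The conclusion rests on two things: that the text describes collection fully, and, for the separation argument, that retraction began on both sides at about the same time. If ratings by side exist, the missing comparator is resolved by saying so, and what remains is that the test should be paired.

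**What to change.** Reconcile the Secondary Outcomes and Statistical analysis sections item by item.

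- **State the rating unit** for intensity and for each interference item: right and left separately, surgical side only, or one rating for the patient.
- **Where both sides were rated**, or still can be at the existing time points, analyse the within-patient difference (MOP side minus control side) with a paired t-test or a signed-rank test in place of the independent t-test.
- **Where only one rating or only a surgical-side rating exists**, report that item descriptively, remove it from the MOP-versus-control test, and make no claim about added pain versus control.
- **Night waking** is best reported per patient unless it was asked by side. Pain on eating need not be excluded if it was rated by side.

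The clarification costs a few sentences and needs no new data. Adding a second rating is possible only if collection is still open, which the past-tense text makes doubtful; it would add slightly to patient burden. Even paired ratings would come from patients who know which side had MOP, since the Blinding section says they could not be blinded. Any side difference should be reported with that limit.

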#### **Statistical analysis (primary and secondary outcomes, subgroup analyses)**

Statistical analysis was accomplished using the Statistical Package for the Social Sciences computer software (SPSS 20.0, SPSS Inc., IL, USA). Probability values equal or less than 0.05 were considered significant. Independent sample t-tests were calculated to analyze the results of the primary outcome and secondary outcomes to compare the difference between MOP and control sides. Similarly, independent sample t-test was performed to compare the amount of root resorption before and after three months in MOP and control sides separately. Chi-square was used for analysis of categorical data including the willingness to repeat the procedure and recommend it to a friend. Descriptive statistics were used to describe the satisfaction and ease of the procedure.

Reliability coefficient (Cronbach's Alpha) was used to evaluate the reliability of measurements of primary outcomes. One examiner did all measurements, and all subjects were randomly selected. Six of 3D superimposed digital models had been chosen randomly. Superimpositions on the rugae area and canine displacement were measured twice within 2-week interval. Reliability coefficient (Cronbach's Alpha) was 0.95, showing excellent superimpositions and measurement agreement.

For intraoral measurements, intra-examiner reliability was done in the lower arch after reaching 0.019x0.025 stainless steel arch wire and teeth were in a passive state; all cases were non-extraction in the lower arch. Six of subjects were selected randomly, and measurements were done twice with the 2-week interval. Measurements were done from the upper mesial wings of the lower canine bracket to the upper distal wing of the lower second premolar bracket. Reliability coefficient (Cronbach's Alpha) was 1.00, indicating excellent measurement agreement.

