### **Sample size calculation**

The sample size was calculated based on a type I error frequency of 5%. According to the power analysis and assuming a large effect size difference between groups (effect size= 0.8), the power analysis yielded 28 subjects per group at a conventional alpha level ( $p = 0.05$ ) and desired power ( $1 - \beta$ ) of 0.90, yielding a total sample size estimate of 56 subjects. All calculations were performed with the computer application G-Power .

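### Root resorption and the periodontal and plaque indices are judged only by p-values; with 28 values per side, a non-significant result could leave an excess of about 0.54 to 1.07 SD on the micro-osteoperforation (MOP) side unexcluded

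*Combined protocol and SAP*

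**What the plan says.** The combined protocol and SAP describes the design thus: "This study was a split mouth randomized clinical trial with a 1:1 allocation". Each patient therefore supplies both a treated and a control side.

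The Secondary Outcomes section states: "Root resorption was evaluated, as a secondary outcome". It is the change in root length in mm between baseline (R1) and three months (R2) on periapical radiographs. The same section adds a periodontal index and a plaque index, scored at the same two times on the upper canines and second premolars.

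The Statistical analysis section gives a single criterion, "Probability values equal or less than 0.05 were considered significant", and applies independent-samples t-tests to primary and secondary outcomes alike. Root resorption also gets a before/after test within each side. Nowhere is a between-side difference with a confidence interval planned, nor a harm margin, nor power for any of these three outcomes.

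The Sample size calculation rests on one assumption, "assuming a large effect size difference between groups (effect size= 0.8", and reports that "the power analysis yielded 28 subjects per group at a conventional alpha level", with power "of 0.90, yielding a total sample size estimate of 56 subjects".

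**The concern.** For a benefit claim, a p-value above the threshold simply means that the claim is not made. For an outcome that could show harm, the useful result is the largest excess that the data rule out, and a p-value alone does not give it. A trial sized for a large difference will often return p above 0.05 when a moderate excess is present. The specified output would then look much the same whether the data excluded a meaningful excess or said little about it.

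Root resorption is the only radiographic harm measure in the plan, so this matters most there. The within-side before/after tests do not fill the gap, because they do not estimate the MOP minus control difference.

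**Working it through.** **Inputs.** From the documents: effect size 0.8, alpha 0.05, power 0.90, 28 per group and 56 in total, split-mouth design, independent t-tests. Assumed, because the documents are silent: two-sided 5% testing, no dropout, one value per side per patient, and between-side correlation ρ of 0.3, 0.5 or 0.7. No outcome SD is given, so results stay in SD units and no mm figure can be stated.

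**The plan's own figure.** For two independent means with d = 0.8, alpha 0.05 and power 0.90, the noncentral t gives:
- one-sided: 27.47, rounded up to 28 per group (power 0.905), which matches the plan;
- two-sided: 33.8, so 34 per group; 28 per group gives power 0.836.

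The stated 28 is thus a one-sided independent-groups figure. It concerns a 0.8 SD difference and no harm outcome in particular.

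**What a non-significant result leaves open.** Let h be the half-width of the 95% interval in SD units. If the observed difference is zero, the upper limit is h. If the MOP side is worse and the result only just misses significance, the observed difference is about h and the upper limit about 2h.

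- Independent: h = t(0.975, 2n−2) × √(2/n)
- Paired: h = t(0.975, n−1) × √(2(1−ρ)/n)

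Planned independent test:
- n = 28 per side: h = 2.005 × 0.2673 = 0.536, so 0.54 to 1.07 SD.
- n = 56 per side (56 patients, both sides each): h = 1.982 × 0.1890 = 0.3745, so 0.37 to 0.75 SD.

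Paired analysis of 28 patients, t(0.975, 27) = 2.052:

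| ρ | √(2(1−ρ)/28) | h | 2h |
|---|---|---|---|
| 0.3 | 0.2236 | 0.459 | 0.918 |
| 0.5 | 0.1890 | 0.388 | 0.776 |
| 0.7 | 0.1464 | 0.300 | 0.601 |

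With 56 patients, the paired limits (h to 2h) are 0.317 to 0.634, 0.268 to 0.536 and 0.207 to 0.415 SD at the same correlations.

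**Chance of missing a true 0.5 SD excess.** For the planned test with 28 per side, the noncentrality is 0.5/√(2/28) = 1.87 on 54 df. Power is 0.451, so the excess is missed about 55% of the time with uncorrelated sides. If the sides are positively correlated, the unpaired test does not benefit: by a normal approximation with ρ = 0.7, power is P(Z > (0.536 − 0.5)/0.146) ≈ 0.40, a miss rate of about 60%. A paired test on 28 patients has power 0.578, 0.723 and 0.909 at ρ = 0.3, 0.5 and 0.7, so it misses 42%, 28% and 9%. With 56 values per side, the independent test has power 0.746 and misses about 25%.

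**The case against.** Several points on the other side are sound.

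- A reader might infer that any non-significant result leaves an excess of the order of 1 SD open. The documents do not support that. The 1.07 SD is the limit for an adverse difference that only just misses significance. At no observed difference it is 0.54 SD, and it is lower still if the difference favours MOP.
- A reader might infer that the sponsor intends to report p above 0.05 as safe, or to withhold means and SDs. No section says either. If side means and SDs were published, an unpaired interval could be formed from them, but not the paired interval that the design calls for.
- A reader might infer that the trial fails a stated safety question. The plan states no safety objective, hypothesis or margin, and it does not label these outcomes as harms. The planned test also keeps 0.836 two-sided power for 0.8 SD, so it is informative about a large excess.
- The sample size is ambiguous. In a split-mouth design, "yielding a total sample size estimate of 56 subjects" could mean 56 sides or 56 patients, and the second reading lowers the limits to about 0.37 to 0.75 SD.
- The indices are scored on two teeth per side, so one value per side holds only if the teeth are combined or analysed separately. The plan does not say.
- Intervals are absent for every outcome, not only these three.

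These points limit the size of the finding and what may be said about intent. They do not supply the missing quantity: under either reading of the sample size, the specified output does not show how much excess has been excluded.

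**Conclusion.** The point holds as a gap in the specified analysis. For three outcomes that could show harm, the plan offers only a p-value from an unpaired test, in a trial sized for 0.8 SD.

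With 28 values per side, a non-significant result with no observed difference or an adverse one could leave about 0.54 to 1.07 SD unexcluded, and a true 0.5 SD excess would be missed about 55% of the time. With 56 patients contributing both sides, the limits are about 0.37 to 0.75 SD. These figures rest on two-sided 5% testing, no dropout, one value per side and, for the planned test, sides treated as uncorrelated. The narrower paired limits (0.46 to 0.92, 0.39 to 0.78 and 0.30 to 0.60 SD with 28 patients) rest on assumed correlations and describe an analysis that the plan does not contain, so they should not be merged with the planned test's range.

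Pairing alone would not settle the matter, since a paired p-value still does not state the excess excluded.

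**What to change.** In the Statistical analysis section, for root resorption (R1 minus R2, mm), periodontal index and plaque index (change from baseline, one value per side per patient), replace the independent-samples comparison between sides with text to this effect:

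*The within-patient MOP minus control mean difference will be reported with its two-sided 95% confidence interval from a paired analysis. Conclusions on harm will be drawn from the upper limit, as the largest excess on the MOP side that the data do not exclude. A p-value above 0.05 will not be reported as showing no difference or as showing safety.*

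The section should also say how the canine and second premolar scores yield one value per side.

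This uses measurements that the plan already specifies and needs no harm margin. It has two costs: the named test for these outcomes changes from independent to paired, and the safety statement is less favourable when the interval is wide.

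### Tested secondary outcomes are judged by the primary's p≤0.05 rule with no adjustment, order or exploratory label; with valid 5% tests, 5 side comparisons give about a 13% to 23% chance of a false positive

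*Combined protocol and SAP*

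**What the plan says.** The section on statistical analysis gives a single threshold: "Probability values equal or less than 0.05 were considered significant". The next sentence names the test: "Independent sample t-tests were calculated to analyze the results of the primary outcome and secondary outcomes to compare the difference between MOP and control sides". The plan separates primary from secondary outcomes by heading. It names no key secondary outcome, no testing sequence and no split of alpha, and it calls none of the secondary results exploratory.

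The Secondary Outcomes section lists what could be compared between sides:

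- Root resorption of the canines over three months.
- Two clinical indices: "Periodontal index and plaque index were also evaluated clinically in both upper" canines and second premolars.
- Pain, from a questionnaire to "assess the pain intensity immediately, after 1 hour, 12 hours, day 1, day 3, day 5 and day 7 following MOP intervention".
- Interference: "Pain interference with daily life was assessed after MOP intervention on 1, 3, 5 and 7 days", with four items (eating, waking at night, discomfort, swelling).

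Not every secondary outcome is tested between sides. Satisfaction and ease are only described. Willingness to repeat and to recommend go to a chi-square test with no control-side comparison described. Root resorption is also tested before against after within each side.

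**The concern.** The secondary outcomes carry the trial's message on harm and acceptability: root length, gingival and plaque status, and pain. Under the stated rule, a p-value of 0.05 or less for one index at one tooth, or for one pain item on one day, may be called significant on the same footing as the primary result. The number of such tests is not stated, so a reader of the results could not tell how many chances there were to find one. Without a label or an adjustment, a chance result could be reported as a conclusion about harm or comfort.

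The point covers the secondary family only. It takes no position on how the primary outcome, measured by two methods over several months, should be reduced to one comparison.

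**Working it through.** **The plan's own figure.** The documents give no family-wise error rate. The only related figure is the sample size: effect size 0.8, alpha 0.05, power 0.90, 28 per group. An unpaired t-test gives 27.5, so 28, if one-sided, and 33.8, so 34, if two-sided. The figure is therefore reproduced by a one-sided unpaired test, although sidedness is not stated. That is a separate matter. What counts here is that the 5% was set for one comparison.

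**Counting the side comparisons** (Secondary Outcomes section):

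- Root resorption: 1.
- Indices: 2 if each is combined over the two teeth, or 2 × 2 = 4 if kept per tooth. Subtotal: 1 + 2 = 3, or 1 + 4 = 5.
- Pain intensity: 7 times.
- Interference: 4 items × 4 days = 16.
- Upper bound: 5 + 7 + 16 = 28. Of these, 23 are pain comparisons that need a control-side rating. (This 28 is unrelated to the 28 per group.)

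The count leaves out the two within-side root tests and the two chi-square tests. These also fall under the threshold but do not compare MOP with control.

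**Tests with a true 5% error.** With no true effect and k independent tests, the chance of at least one false positive is 1 − 0.95^k:

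- k = 3: 1 − 0.8574 = 14.3%
- k = 5: 1 − 0.7738 = 22.6%
- k = 28: 1 − 0.2378 = 76.2%

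Outcomes in the same patient are probably correlated. The documents give no value, so a range is assumed. Simulated equicorrelated two-sided tests give:

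| Correlation between outcomes | 5 tests | 28 tests |
|---|---|---|
| 0 | 22.6% | 76.2% |
| 0.5 | 18.1% | 49.2% |
| 0.8 | 12.7% | 25.1% |

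For 3 tests the range is about 14% at correlation 0 to 10% at 0.8. A second simulation, with paired t-tests on an assumed 28 patients, agrees closely (at 0.5: 18.6% and 51%). The expected number of false positives is k × 0.05 at any correlation: 0.25 for 5 tests and 1.4 for 28.

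**The planned independent t-test.** The two sides belong to the same mouth. If they correlate at r, the variance of the difference is (1 − r) times what the independent test assumes. For large samples the two-sided error per test is 2[1 − Φ(1.96/√(1 − r))]:

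- r = 0: 5.0%
- r = 0.3: 1.96/0.837 = 2.34, giving 1.9%
- r = 0.5: 1.96/0.707 = 2.77, giving 0.56%

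With independent outcomes and r = 0.3, the family-wise rate is 1 − 0.98085^3 = 5.6% for 3 tests, 9.2% for 5 and 41.8% for 28. At r = 0.5 it is 1 − 0.99443^3 = 1.7%, 2.8% and 14.5%. It falls to 5% at r of about 0.42 for 5 tests and 0.60 for 28. With outcome correlation 0.5, simulation at 28 patients gives about 8% (5 tests) and 26% to 27% (28 tests) at r = 0.3, and about 3% and 11% to 12% at r = 0.5.

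**The case against.** Four arguments stand against the point.

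First, a reader might infer that the plan as written has a family-wise error well above 5%. The documents do not establish that. The planned test ignores the pairing and is conservative when the sides correlate positively; at a side correlation of 0.5, five tests stay near 3%. This stands as a limit on the claim. It is not a safeguard, because the correlation is not given, the protection is a by-product of a test that does not fit the design, and it disappears once a paired test is used.

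Second, a reader might take 28 as the number of tests. The text does not say so. It records pain after the MOP procedure, asks about swelling on the operated side, and describes no separate control-side rating. Waking at night is hard to assign to a side. The figure of 28 is an upper bound, and the firm count is 3 to 5.

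Third, the null is doubtful for early pain. Only one side is perforated, so a difference there may be real and a rejection would then be correct. The 1.4 expected false positives apply only if nothing differs.

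Fourth, trials commonly leave secondary outcomes unadjusted, and this plan nowhere calls them confirmatory. That is fair, but it does not call them exploratory either, and it gives them the same significance rule as the primary. The missing label is what remains of the concern.

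**Conclusion.** The point holds as a cheap improvement to what may be concluded from the secondary outcomes. Every secondary outcome that is tested is judged at p≤0.05 with nothing to limit the claims, and the number of tests is not stated.

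On a test with a true 5% error, the chance of at least one false positive is about 10% to 14% for 3 comparisons, 13% to 23% for 5 and 25% to 76% for 28. These figures assume no true effect on any secondary outcome and equal correlations between outcomes from 0.8 down to 0. Under the planned independent t-test the rate may be higher or lower than 5%, and the documents do not allow it to be fixed.

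It would be wrong to read the plan as declaring every secondary outcome significant. It sets a threshold, tests some of the outcomes and only describes others. The primary conclusion is not affected.

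**What to change.** In the statistical analysis section, state that p≤0.05 decides the primary comparison only. Report all secondary outcomes, root resorption included, as exploratory. Where both sides are measured, give the within-patient difference (MOP minus control) with a 95% confidence interval and make no significance claim. State that the intervals are not adjusted for multiplicity, because an unadjusted interval that excludes zero carries the same information as p<0.05. State also how many side comparisons are made, whether the indices are combined over teeth, and whether pain is rated for the control side.

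If a confirmatory secondary claim is wanted, name the set and apply Holm's method across it. The smallest p-value would then face 0.05/3 = 0.0167 for 3 tests, 0.05/5 = 0.01 for 5, or 0.05/28 = 0.0018 for 28. The root-resorption analysis should not depend on the efficacy result, since it is a harm outcome and is of interest whether or not MOP speeds tooth movement.

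The cost is a few sentences, with no extra patients or data. Isolated p-values of 0.05 or less for pain, the indices or root length could no longer be called significant, but every estimate is still reported, so no harm signal is hidden. The section is written in the past tense and already reports reliability results. If outcome data have been seen, a named confirmatory set could not be presented as prespecified, whereas the exploratory label would remain honest.
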